University of Iowa

SAFETY OF 2-WEEK USE OF AEROSOLIZED
XYLITOL IN SUBJECTS WITH CYSTIC
FIBROSIS

NCT Number 00928135

[name]
3-16-2012

SAFETY OF 2-WEEK USE OF AEROSOLIZED XYLITOL IN SUBJECTS WITH CYSTIC
FIBROSIS

ABSTRACT

Cystic fibrosis (CF) lung disease is characterized by chronic bacterial colonization and recurrent infection of the airways. Disruption of the cystic fibrosis transmembrane conductance regulator chloride channels in subjects with CF results in altered fluid and electrolyte transport across the airway epithelium thereby initiating infections. Lowering the ASL salt concentration and increasing the ASL volume might therefore potentiate innate immunity and therefore decrease or prevent airway infections in subjects with CF. Xylitol is a 5-carbon sugar that can lower the airway surface salt concentration, thus enhancing innate immunity. We recently tested the safety and tolerability of inhaling increasing concentrations of single doses of hypertonic xylitol (10% followed by 15%) in stable subjects with CF. All six subjects tolerated both the doses well. There was no significant change in FEV₁ or respiratory symptom score. In this protocol, we propose to test the safety and tolerability of aerosolized xylitol used daily for 2 weeks in subjects with cystic fibrosis. In a pilot, 2-week study, 60 subjects with cystic fibrosis with an FEV₁ >30% predicted will be randomized to receive aerosolized 7% hypertonic saline (4 ml) or 15% xylitol, (5 ml) twice a day for 14 days. The primary outcomes will be safety as assessed by FEV₁ change from baseline, adverse events and respiratory symptom score. Outcomes for trend in efficacy include density of colonization per gram of sputum, time to next exacerbation, sputum cytokines and revised CF quality of life questionnaire.

BACKGROUND

Cystic fibrosis (CF) lung disease is characterized by chronic bacterial colonization and recurrent infection of the airways. Disruption of the cystic fibrosis transmembrane conductance regulator chloride channels in subjects with CF results in altered fluid and electrolyte transport across the airway epithelium thereby initiating infections [1, 2]. These infections eventually destroy the lungs and contribute to significant morbidity and mortality in patients with CF. It is well known that antibacterial activity of innate immune mediators such as lysozyme and beta defensins in human airway surface liquid (ASL) is salt-sensitive; an increase in salt concentration inhibits their activity [3]. Conversely, their activity is increased by low ionic strength [4-6]. Lowering the ASL salt concentration and increasing the ASL volume might therefore potentiate innate immunity and therefore decrease or prevent airway infections in subjects with CF.

Xylitol, a five-carbon sugar with low transepithelial permeability, which is poorly metabolized by bacteria can lower the salt concentration of both cystic fibrosis (CF) and non-CF epithelia *in vitro* [7]. Xylitol is an artificial sweetener that has been successfully used in chewing gums to prevent dental caries [8, 9]; it has been used as an oral sugar substitute without significant adverse effects [10]. It has also been shown to decrease the incidence of acute otitis media by 20-40% [11]; nasal application to normal human subjects was found to decrease colonization with coagulase negative staphylococcus [7].

We found that aerosolized iso-osmolar xylitol was safe in mice and healthy volunteers when administered over a single day [12]. We then tested the safety of a single dose aerosolized iso-osmotic xylitol in subjects with stable CF and found that it was well tolerated [13]. In a study of pharmacokinetics of aerosolized xylitol in normal volunteers, the terminal half-life of a single dose of iso-osmotic xylitol (10 mL) was 45 minutes [14]. In a recent study, we observed that single doses of 10% followed by 15% xylitol was well tolerated by subjects with cystic fibrosis who were stable (safety reported submitted to the FDA).

We conducted a 2 week toxicology study under good laboratory practices done in rats and dogs in collaboration with Lovelace Respiratory Research Institute (manuscript in preparation). Aerosolized xylitol was generated from a 450 mg/mL nebulizer solution through two Aerotech II nebulizers. Exposure levels were defined by time of exposure (high, 3 hours; mid, 1.5 hours, and low, 0.5 hours). Mean xylitol aerosol concentrations were 3.14 ± 0.19 mg/L for the 3-hour (high) exposure group, 3.03 ± 0.12 for the 1.5-hour (mid) exposure group, and 2.91 ± 0.18 for the 0.5-hour (low) exposure group. Mean particle sizes of xylitol were determined to be in the inhalable size range for rodents [(range 1–3) μm mass median aerodynamic diameter]. Mean total inhaled doses were estimated as 354.2 (target of 394.8), 170.9 (target of 197.4), and 54.7 (target of 65.8) mg/kg, for the high, mid, and low exposure groups, respectively. Mean total deposited doses were estimated as 37.55 (target of 55.27), 18.12 (target of 27.64), and 5.80 (target of 9.21) mg/kg, for the high, mid, and low exposure groups, respectively.

All rats survived to the scheduled necropsy. Xylitol exposures were generally well-tolerated. No specific xylitol-related findings were observed in clinical signs, body

weights, organ weights, or histopathology. Single and 14 consecutive-day xylitol exposures were associated with a resolvable discoloration of lungs in rats sacrificed prior to 24 h after exposure. Non-specific inflammatory and remodeling responses of the upper airway were observed after 14 days of exposure. The latter is commonly observed in rodent inhalation studies and was not determined to be related to any specific chemical toxicity of xylitol. A No Observed Effect Level (NOEL) was not determined based on the acute pulmonary findings. The No Observed Adverse Effect Level (NOAEL) was determined to be the low exposure level due to the resolvable nature of the acute gross pulmonary findings and the lack of any corroborating pulmonary histopathology in main study and recovery animals at all exposure levels.

For the dog study, beagle dogs were exposed to aerosolized xylitol for varying durations (high exposure group at 1 hour, mid exposure group at 0.5 hours, and low exposure group at 0.25 hours). A control group was exposed for 1 hour to a nebulized normal saline solution. Mean xylitol aerosol concentrations were 3.49 ± 0.15 mg/L for the high exposure group, 3.55 ± 0.18 for the mid exposure group, and 3.54 ± 0.18 for the low exposure group. Mean particle sizes of xylitol were determined to be in the inhalable size range for dogs [(actual range 2–3) μm mass median aerodynamic diameter]. Mean total inhaled doses were estimated as 105, 53, and 27 mg/kg, for the high, mid, and low exposure groups, respectively. Mean total deposited doses to the pulmonary region were estimated as 21, 11, and 5 mg/kg, for the high, mid, and low exposure groups, respectively.

All dogs survived to the scheduled necropsy and xylitol exposures were generally well-tolerated. No treatment-related findings were observed in clinical signs, body

weights, physical (with ECGs) and ophthalmic examinations, food consumption, clinical pathology, gross pathology, organ weights, or histopathology. The No Observed Effect Level (NOEL) was determined to be the high exposure level.

In this pilot study we propose to test the hypothesis that aerosolized hypertonic xylitol given twice daily for 2 weeks, will be safe and well tolerated and potentially lower the density of colonization in subjects with CF compared to hypertonic saline. We chose hypertonic concentration of xylitol to be comparable in part to hypertonic saline which is being offered as a routine treatment in hospitalized patients with CF exacerbation. In addition, hypertonic concentration allows us to deliver adequate amounts of xylitol with twice a day dosing which will help with compliance.

Protocol

Randomized Controlled Study of Aerosolized hypertonic xylitol versus hypertonic saline in hospitalized patients with exacerbation of cystic fibrosis

The study has been approved by the University of Iowa Institutional Review Board as well as the Food and Drug Administration. This will be a randomized, controlled study. Blinding is not assured because of ability to taste the sweetness of xylitol.

Inclusion Criteria: Subjects with CF (medical record evidence of cystic fibrosis transmembrane conductance regulator mutation or sweat chloride test or nasal voltage difference, **and** 1 or more clinical findings of CF), age 12 or greater with an FEV₁ >30% predicted (within the last 14 days) and oxygen saturation \geq 90% on FiO₂ \leq 50%, admitted for an exacerbation, able to provide written informed consent or assent.

Exclusion Criteria: Pregnancy, hemoptysis more than 60 mL within the last 30 days, use of any investigational study drug within the last 30 days, initiation of hypertonic saline within the last 30 days, known intolerance to hypertonic saline, serum creatinine 2 mg/dl or more, active malignancy in the last year, on waiting list for lung transplantation, received a solid organ transplant, lack of FEV₁ data from the last 14 days and previous participation in this study.

Experimental Treatment: Aerosolized 15% xylitol, 5 ml twice a day for 2 weeks using Pari LC nebulizer with Vios compressor, (Pari Inc, Monterey, CA) . Xylitol crystals are

made as food additives by Danisco Cultor, USA. Aerosol solution is sterile, non-pyrogenic, preservative-free solution for inhalation made by UI Pharmaceuticals (Iowa City, IA).

Control Treatment: Hypertonic 7% saline (UIHC pharmacy) 4 ml twice a day for 2 weeks using the same kind of nebulizer.

Screening and Baseline Visit: On the day of admission for exacerbation, informed consent obtained in subjects whose admission spirometry (or spirometry within the last 14 days prior to admit date) shows an FEV₁ >30% predicted. Once consented, subjects will be randomized to either xylitol or saline group as per the randomization code previously generated by the statistician. Demographics, current medications use and the revised CF quality of life questionnaire (CFQ-R) will be completed. Spontaneously expectorated sputum will be collected and processed for cell count and cytokines and quantitative cultures. Blood will be collected for chemistry and liver function tests (LFT). Pregnancy test will be done in women. All medication use during hospitalization will be recorded. Treatment will begin the day after admission for an exacerbation. Results from spirometry that is routinely done twice a week for inpatients will be recorded. All spirometry testing will follow the 2005 American Thoracic Society guidelines.

First dose pre and post spirometry: All subjects will undergo spirometry before and 20 minutes after the first study drug dose as follows.

Perform baseline spirometry and measure SpO₂. Multiply the patient's best FEV₁ by 0.80 to obtain 20% fall in FEV₁ value.

Premedicate subject with 4 puffs albuterol and wait 15-30 min.

Begin study drug nebulization.

Wait for 15-30 minutes and repeat spirometry and SpO₂.

Subject is excluded from the study if SpO₂ is <89% or FEV₁ declines by 20% or greater from baseline.

Administration: Subjects will take their routine inhaled medicines followed by chest physical therapy. All subjects will then receive 2-4 puffs of albuterol metered dose inhaler 15-30 minutes before the study drug. Finally the study drug will be inhaled. All empty, unused and partially used study drug containers will be tracked by the investigators. Subjects will be required not to use any new treatments if not medically indicated during the study period.

Day 14 follow-up: Subjects will undergo spirometry and sputum collection and answer CFQ-R questionnaire. Blood draw for LFTS and electrolytes will be done if not done for clinical reasons. If subjects are discharged prior to 14 days of xylitol use, nebulizer solutions will be sent home. They will be asked to keep a log of nebulizer use and bring back empty and unused vials on follow-up visit (Day 10-15, preferably day 14). They will undergo spirometry and sputum collection and questionnaire administration on that day. If subjects don't return on this day, they will have a phone follow-up for adverse events and compliance.

Phone follow-up: Week 1, Day 90 and Day 180 after discharge: Subjects will be contacted by phone at these time points to enquire about further pulmonary exacerbations, admissions, and other AEs.

In the event of bronchospasm: Subjects will alert the nurses or study team members. Nebulized bronchodilators will be immediately administered. Once symptoms resolve, they will undergo spirometry using a portable handheld spirometer by a trained user. If the subjects dropped FEV₁ by 20% or greater from their baseline, they will not receive further study drug. However, they will remain in the study for completion of data collection.

Endpoints: Primary outcome will be FEV₁ change from baseline. Other safety assessments include vital signs within 30 minutes after nebulization, withdrawal from the study, rescue bronchodilator use, incidence of treatment related adverse events, and laboratory tests (chemistry and liver function tests). Efficacy outcomes include difference in density of colonization per gram of sputum from baseline to day 14, time to next hospitalization, difference in CFQ-R, sputum cytokine levels and cell counts.

Adverse events such as cough, chest tightness, and headache will be scored on a visual analog scale. Other variables collected include antibiotic and other medication use during the hospitalization, demographics, organ involvement with CF, genotype data from medical records. Follow-up phone calls will be made 1 week, 3 months and 6 months

after study completion for any complications and to assess the time to next hospitalization.

Adverse events: Any untoward medical occurrence (abnormal symptom, sign or laboratory value) in a study subject that is temporally associated with the study drug will be reported as an adverse event. The event does not have to have a causal relationship with the treatment. The event will be classified by the investigator as mild, moderate or severe. The relationship of an adverse event to the study drug will be determined by the investigator to be ‘unlikely to be related, possibly related, probably related or definitely related’.

Future Use of Stored Specimens

Subjects will be asked for permission to keep any remaining unlinked sputum and blood specimens for possible use in future research studies. Samples may be shared with other investigators at other institutions. The samples will not be sold or used directly for production of any commercial product. No human genetic tests will be performed on samples. Each sample will be labeled only with a study ID to protect subject’s confidentiality.

There are no benefits to subjects in the future research use of their specimens. Reports about future research done with these samples will not be kept in their health records.

Subjects can decide if they want their samples to be used for future research or have their samples destroyed at the end of the study. A subject’s decision can be changed at any time prior to the end of the study by notifying the study investigators in writing.

However, if a subject consents to future use and some of their specimens have already been used for research purposes, the information from that research may still be used.

Statistical analysis: We plan to enroll a total of 60 subjects for this study. These subjects will be randomly assigned to the treatment (xylitol) and control (saline) groups, with a goal of 30 subjects in each group. Since this is a pilot safety study, it has been primarily powered to detect common adverse events. Assuming that the likelihood of a subject experiencing an adverse event is no less than 5%, a sample size of 30 subjects ensures 80% power towards event detection [16]. (In other words, with a group sample size of 30, the probability of observing at least one adverse event in the group is at least 80%.)

Study Performance

Accrual will be assessed on a monthly basis. We will examine the number of screened subjects, those meeting eligibility criteria, the number of persons consenting to participate and the number of randomized. The rate of accrual will be tracked versus the expected number to achieve the target of 60 participants randomized.

We will also track the completion number and proportion by time. The number of study terminations and reason for termination will be measured. The subject will undergo a spirometry and if the FEV₁ has declined by 20%, the subject will be terminated from the study.

Baseline

The composition of the study sample will be described in aggregate. Comparison of randomized participants of baseline characteristics will be analyzed using 2 sample t-test,

Wilcoxon rank sum test, and analysis of variance (ANOVA) as indicated by the type and characteristics of the variable.

Outcomes

To assess the adequacy of these group sample sizes for testing a trend in efficacy, we consider the outcome of log CFU. We assume an average density of colonization of 6.5 log CFU with a SD of 1.5 log CFU among CF subjects. To detect a reduction of 1.5 log CFU in the xylitol group with 80% power, the required sample size is 17 subjects per group. (This computation is based on a two-sided, two-sample t-test conducted at the 0.05 level of significance.) Data from all patients who have received at least one dose of the drug or placebo will be analyzed. Thus, the analysis will be based on intention to treat. All tests will be two-sided, and conducted using a significance level of 0.05.

The primary outcome is FEV₁ change from baseline. To test for a difference in the mean change between the treatment group and the control group, a two-sample t-test will be conducted. To estimate the difference in the mean change, the equivalent confidence interval procedure will be used. Prior to conducting the test, normality will be assessed for each group based on normal probability plots. If gross departures from normality are observed, a Wilcoxon rank sum test will be performed instead of the t-test. (With group sample sizes of 30, the t-test is fairly robust to departures from normality.)

The same analytical approach will be used to assess differences in the group means for the following variables: the primary outcome of change in respiratory symptom score, and the efficacy outcomes of change in density of colonization (per gram of sputum),

change in sputum cytokines and cell counts, and responses to all Likert-scale questions on the CFQ-R.

To analyze group differences in the efficacy outcome of time to next exacerbation, a time-to-event analysis will be conducted. Kaplan-Meier estimates will be obtained for each survival curve (where failure is defined by exacerbation). To compare the survival distributions, a log rank test will be employed.

To compare the proportion of subjects in each group who have experienced any adverse events, Fisher's exact test will be used. Since certain subjects may experience multiple adverse events, we will also compare the incidence of adverse events in each group. For this comparison, a test will be conducted to contrast the mean number of events in each group, where the two samples of event counts are treated as arising from independent Poisson distributions. To estimate the difference in group proportions and the difference in group means, equivalent confidence interval procedures will be employed.

The preceding inferential procedures will be conducted for individual types of adverse events (e.g., cough, chest tightness, headache), as well as the aggregate of all adverse events. Fisher's exact test will also be used to compare the compliance proportion and the proportion of rescue bronchodilator use in each group.

Since this study is a randomized, controlled clinical trial, we expect the treatment group and the control group to be balanced with respect to factors that could affect the primary

and efficacy outcomes, such as age and gender. For such variables, descriptive statistics will be compiled for each group to ensure that the randomization has been effective. If a marked difference is observed in the distribution of any variables, an analytical approach will be utilized that will allow us to control for these variables. Specifically, the t-test can be replaced with an analysis of covariance model, the log-rank test can be replaced with a Cox proportional hazards model, Fisher's exact test can be replaced with a logistic regression model, and the two-sample Poisson test can be replaced with a Poisson regression model.

All analyses will be performed by the study statistician using SAS version 9.2 (SAS Institute, NC).

Risks: Exposure to xylitol and hypertonic saline is expected to not elicit any significant symptoms other than some cough; however we recognize that there may be a possibility of bronchospasm with the hyperosmolar xylitol in a subgroup of subjects with CF who have bronchial hyperresponsiveness that was not known previously.

Blood draw and spirometry are a part of standard care and will not pose added risks.

With the admission labs that are routinely done, we will collect another red top tube for liver function tests if they were not planned. Answering questions may involve some concentration and may be boring.

Risks are minimized as follows: In the event of bronchospasm with the study drug, immediate treatment with bronchodilators is available. The subject will undergo a spirometry and if the FEV₁ has declined by 20%, the subject will be terminated from the

study. Blood draw will be performed by trained nurses or the hospital IV team with minimal discomfort. Spirometry will be done by experienced respiratory therapists. Symptom questionnaire will be administered by well-trained interviewers and will be as brief as possible.

Confidentiality: All the test results and questionnaire will be stored in the research office under lock and key with access only to the investigators. Once all testing is complete and data is entered for analysis, there will be no identifiers connecting the subject to the data. All results will be reported in summary without identifying the subjects. Blood and urine specimens will not be stored for future use.

Stopping criteria: If any subject drops his/her FEV₁ % predicted by 20%, we will stop further exposures. If 3 subjects drop their FEV₁ by 20% the treatment assignment will be unblinded and they were all in the xylitol group, the study will be closed for further recruitment.

Safety Monitoring: Any unexpected fatal or life-threatening adverse event will be reported to the Food and Drug Administration (FDA) by phone, fax or email no later than 7 days of occurrence. Any other serious and unexpected adverse event associated with the use of xylitol will be reported to the FDA within 15 days of occurrence. Please see DSMP for a detailed safety plan.

REFERENCES

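### Blinding is not defined by role: those who measure and analyse the effort-dependent primary outcome are not masked, and the blinding caveat and the stopping criteria do not agree

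*Combined protocol and SAP*

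**What the plan says.** The design paragraph under the Protocol title describes a randomized, controlled study and adds "Blinding is not assured because of ability to taste the sweetness of xylitol". It does not call the trial open-label, and it names no role as masked or unmasked.

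Under Stopping criteria: "If 3 subjects drop their FEV₁ by 20% the treatment assignment will be unblinded". This presumes that someone is still blinded at that point.

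On who produces and handles the data:

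- **Primary outcome.** "The primary outcome is FEV₁ change from baseline" (Outcomes). The same section also labels the change in respiratory symptom score a primary outcome, whereas Endpoints lists FEV₁ change alone.
- **Measurement.** "Spirometry will be done by experienced respiratory therapists" (Risks are minimized as follows). Trained interviewers give the symptom questionnaire. All spirometry is to follow the 2005 American Thoracic Society guidelines (Screening and Baseline Visit).
- **Allocation.** Subjects are randomized "as per the randomization code previously generated by the statistician" (Screening and Baseline Visit).
- **Analysis.** "All analyses will be performed by the study statistician using SAS version 9.2". The test depends on normal probability plots drawn for each group: "If gross departures from normality are observed, a Wilcoxon rank sum test will be performed instead of the t-test". Covariates enter if a marked imbalance appears, and no threshold is given.

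**The concern.** Taste unmasks the person who inhales. It does not by itself unmask the therapist coaching the forced expiration, the interviewer, the laboratory or the analyst. FEV₁ depends on effort and on how hard the operator pushes for it, so an operator who knows the arm can shift the primary outcome without intending to.

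A statistician who holds the code, looks at plots by group and then judges whether departures are gross or imbalances marked is making analysis decisions with the arms visible.

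In a safety comparison against an active control, such bias could create a difference or hide one.

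**Working it through.** **1. The two statements on blinding, side by side.** The design paragraph says blinding cannot be assured, for a reason that applies to subjects. The stopping criteria describe breaking a blind. Both can be true only if some roles are masked and others are not. The documents never say which, so the two must be reconciled role by role.

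**2. Which role bears on which outcome.**

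| Role | Outcome exposed | Masking stated? |
|---|---|---|
| Spirometry operator | FEV₁ change | No |
| Interviewer | Symptom score, CFQ-R | No |
| Sputum laboratory | Colonization density, cytokines, cell counts | No; labelling by study ID alone appears only under Future Use of Stored Specimens |
| Investigator grading adverse events | Severity and causality | No; investigators also track drug containers (Administration) |
| Statistician | All, through choice of test and covariates | No |

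Only the operator and the statistician bear on FEV₁. Masking the laboratory or the interviewer protects other outcomes.

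**3. Assessor bias, illustration.** The plan gives no figure to reproduce here. From the documents: n = 30 per arm, two-sided α = 0.05, two-sample t-test. Assumed: a systematic between-arm bias of b SD in FEV₁ change, and no true difference.

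Noncentrality δ = b·√(n/2) = b·√15 = 3.873b, with df = 58 and critical value 2.002.

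Rejection probability = P(T > 2.002) + P(T < −2.002), where T is noncentral t with df 58 and noncentrality δ.

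| b (SD) | δ | Rejection probability |
|---|---|---|
| 0 | 0 | 5.0% |
| 0.1 | 0.387 | 6.7% |
| 0.2 | 0.775 | 11.9% |
| 0.3 | 1.162 | 20.8% |

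**4. Analyst choice of test, upper bound.** Trials with no true difference and 30 per arm were simulated, and the smaller of the t-test and Wilcoxon p-values was always taken. Runs of 20,000 trials gave a type I error of 5.6% to 6.0%. The plan does not allow this search, so about 6% is a ceiling for this step.

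**The case against.** The protocol's caveat is candid, and it does not abandon blinding. A reader might infer that masking was dropped for everyone. The wording is only that it is not assured, and the stopping criteria imply that some masking was intended. The supportable defect is that roles are undefined and the two statements do not fit together.

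A reader might also infer that masking costs nothing. The documents show obstacles:

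- Subjects discharged early bring vials to the visit at which spirometry and the questionnaire are done.
- The volumes differ (5 ml v 4 ml).
- Subjects can say what they tasted.
- A/B labels do not mask a statistician who made the list unless someone else recodes it.

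Safeguards exist. Spirometry follows a published standard and is done by experienced staff. The t-test is the named default, normality is judged before testing, and covariate adjustment is triggered by baseline imbalance and not by p-values. A reader who takes the smallest p-value over tests and covariates can obtain type I error of 8% to 9%, but the plan permits no such search. Allowing only covariates imbalanced at an assumed p < 0.10, and still taking the smallest p-value, gave roughly 5% to 7%.

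The false-positive figures also do not measure missed harm, which matters most in a safety pilot.

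All of this stands, and it narrows the point without removing it. A spirometry standard governs technique and does not conceal the arm. A baseline trigger with no threshold still calls for judgement, and nothing requires that judgement to be made before the arms are visible.

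**Conclusion.** The concern holds in this limited form. The blinding caveat and the stopping criteria must be reconciled. No role that measures or analyses FEV₁ is masked, and the statistician who generates the code appears also to analyse, with discretion over test and covariates. That the two are one person is a reading of the text; the documents do not say so outright. The safety plan cited under Safety Monitoring is not in the documents and might say more, but the protocol itself should name the masked roles.

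The size is unknown. The range of about 7% to 21% rests wholly on an assumed bias of 0.1 to 0.3 SD, and the ceiling of about 6% on an adverse choice of test. Neither is evidence that bias will occur. Bias in the other direction could mask harm; this was not quantified. The documents do not support a claim that the primary result will be biased, only that an avoidable route to bias is left open.

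**What to change.** 1. In the design paragraph, list which roles may know the arm, including the investigator who grades adverse events, and align the wording of the stopping criteria with that list.
2. Have Day 14 spirometry done by existing staff who are not told the arm and did not nebulize that subject. Do the same for the questionnaire, to protect the symptom score and CFQ-R. Ask subjects not to mention taste, and have someone else receive returned vials.
3. Send sputum to the laboratory under study ID only. This protects the sputum outcomes, not FEV₁.
4. Have the pharmacy, or another person outside the analysis, relabel the arms A/B and replace the subject identifiers, so that the generated list does not reveal the arm. Release the key once the normality and covariate decisions are recorded and dated.

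Cost: protocol wording, some scheduling and a relabelling step. No extra subjects, visits or tests are needed, and the sample size and treatments are unchanged. Masking of the operator and interviewer will be imperfect because subjects may disclose taste and the volumes differ. Reporting by subjects who know their own arm is not cured.

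### Home doses have no prospective record of symptoms or rescue bronchodilator use, although rescue use is compared between arms

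*Combined protocol and SAP*

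**What the plan says.** **Home dosing.** Under Day 14 follow-up: "If subjects are discharged prior to 14 days of xylitol use, nebulizer solutions will be sent home". For these subjects, "They will be asked to keep a log of nebulizer use and bring back empty and unused vials" at a visit between Day 10 and Day 15. Of that visit the section says: "They will undergo spirometry and sputum collection and questionnaire administration on that day". If the visit is missed, a phone call covers adverse events and compliance.

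**What is recorded, and where.** Screening and Baseline Visit states: "All medication use during hospitalization will be recorded". Endpoints repeats the limit to the hospital stay. The twice-weekly spirometry to be recorded is the routine testing of inpatients.

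**Response to bronchospasm.** The bronchospasm paragraph reads: "Subjects will alert the nurses or study team members. Nebulized bronchodilators will be immediately administered". A trained user then performs handheld spirometry, and a fall of 20% or more ends study drug. The risk-minimization paragraph says, without limiting it to the hospital: "In the event of bronchospasm with the study drug, immediate treatment with bronchodilators is available".

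**Use of the data.** Endpoints lists rescue bronchodilator use among the safety assessments. Under Outcomes, Fisher's exact test compares "the compliance proportion and the proportion of rescue bronchodilator use in each group". Stopping criteria act on a 20% fall in any one subject, and close recruitment if three subjects have such a fall and all were on xylitol.

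**Later contact.** Phone follow-up places a Week 1 call after discharge. Endpoints places the one-week call after study completion. Safety Monitoring refers to a separate DSMP.

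**The concern.** Bronchospasm is the main drug-related risk that the protocol names, and this is primarily a safety study. Some of the 14 days of dosing may take place at home. There, the plan names no form on which a subject notes wheeze, chest tightness or use of a rescue bronchodilator, and it schedules no spirometry between discharge and the Day 10-15 visit.

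Three things are at stake:

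- The rescue-use comparison may cover inpatient doses only, or may mix recorded inpatient use with recalled home use. Nothing says which.
- Home symptoms rest on recall. The protocol concedes that blinding is not assured, so recall can be coloured by knowledge of the treatment.
- A short-lived 20% fall in FEV1 at home, or any fall in a subject who misses the visit, may not reach the stopping criteria.

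**Working it through.** **1. The plan's own safety figure.** Statistical analysis assumes an adverse event risk of at least 5% per subject and 30 subjects per group, and states 80% probability of seeing at least one event. Check: 1 − 0.95^30 = 0.785, which agrees within two points.

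That figure presumes that every event is captured. Let f be the share of events that occur at home and c the share of those captured. Neither is in the documents, so both are assumed. The probability becomes 1 − (1 − 0.05 × [1 − f(1 − c)])^30:

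| Home share f | c = 0 | c = 0.5 | c = 1 |
|---|---|---|---|
| 10% | 0.749 | 0.768 | 0.785 |
| 25% | 0.682 | 0.739 | 0.785 |
| 50% | 0.532 | 0.682 | 0.785 |

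**2. Data sources side by side.**

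| Item | In hospital | At home, before the Day 10-15 visit |
|---|---|---|
| Doses taken | Containers tracked | Log and vial return |
| Rescue bronchodilator | Medication record | None named |
| Symptoms, bronchospasm | Alert to nurses or study team | Alert to study team possible; otherwise recall at visit or call |
| FEV1 | Routine, twice a week | None scheduled |

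The gap is clearest for rescue use. The calls are described as covering exacerbations, admissions, adverse events and compliance, and rescue use is not listed.

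**3. Doses at home.** Twice daily for 14 days is 28 doses. Discharge at the end of treatment day d leaves 28 − 2d at home. The discharge days are assumed: d = 5 leaves 18 (64%), d = 7 leaves 14 (50%), d = 10 leaves 8 (29%).

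**4. Effect on recorded rescue use.** Assume that 30% of subjects need rescue at least once over 28 doses, at constant risk per dose. If nothing is captured at home, the recorded proportion is 1 − 0.70^(2d/28). If half of home use is captured, it is about 1 − 0.70^([2d + 0.5(28 − 2d)]/28).

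| Discharge day d | No home capture | Half captured | Full capture |
|---|---|---|---|
| 5 | 12.0% | 21.5% | 30% |
| 7 | 16.3% | 23.5% | 30% |
| 10 | 22.5% | 26.3% | 30% |

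**5. Timing of the Week 1 call.** If it is counted from discharge, the call falls at about day d + 7, which is day 12, 14 or 17 for d = 5, 7 or 10. If it is counted from completion on day 14, it falls at about day 21, after home dosing ends.

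**The case against.** The plan does not leave home dosing without follow-up, and a reader could easily infer more than the text supports.

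- **That home events go unmonitored and uncounted.** The documents do not support this. They provide the Day 10-15 visit with spirometry and questionnaire, a fallback call for adverse events, and a Week 1 call. The adverse event definition rests on timing relative to study drug, with no limit to the hospital. What remains is that capture depends on recall.
- **That FEV1 falls at home cannot count toward the stopping criteria.** Those criteria carry no limit on setting. A fall that persists to the visit would be measured there and could count, though late for the individual subject. The gap is confined to transient falls and missed visits.
- **That no part of the bronchospasm response applies at home.** Subjects may alert study team members as well as nurses. Administration also has all subjects take albuterol by inhaler before study drug, so a bronchodilator is probably at hand. The steps with no described home route are staff-given nebulized treatment and handheld spirometry.
- **That unequal stays bias the arm comparison.** This is possible, but no stay data are given and no difference between arms is shown.
- **That rescue use is meant to cover all 28 doses.** Neither Endpoints nor Outcomes states the period. That silence is itself part of the problem.

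First-dose reactors are removed after supervised spirometry, and the risk is placed in a hyperresponsive subgroup. Both suggest that risk may be higher early, in hospital, so constant risk per dose probably overstates the loss. Finally, the DSMP was not supplied and may cover home monitoring. It would settle that part, but would not by itself correct the unqualified statement on immediate treatment or the hospital-only medication record.

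**Conclusion.** The point holds as a cheap improvement, with medium confidence. In the supplied text, home rescue bronchodilator use has no named data source although it is compared between arms. Home symptoms have no prospective record, and no spirometry is scheduled between discharge and the Day 10-15 visit. The two anchors for the Week 1 call conflict, so that contact cannot be relied on to fall within the dosing period.

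The size is unknown. The 12.0%, 16.3% and 22.5% are a worst case that rests on an assumed 30% risk, constant risk per dose, assumed discharge days and no capture at home; with half captured the shortfall is much smaller. The 0.532 to 0.785 range for seeing an adverse event depends likewise on assumed home share and capture. None of these is an estimate of what the trial will lose, and the sample size reasoning is not in dispute.

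**What to change.** 1. Add two per-dose columns to the existing home log: wheeze or chest tightness, and rescue bronchodilator use (yes/no). Word the second so that the routine albuterol taken before each dose is not counted as rescue.
2. Review the log at the Day 10-15 visit, or go through it with the subject in the fallback call.
3. State the period for the rescue-use comparison. Analyse it over all doses, and also report inpatient and home doses separately.
4. Reconcile the bronchospasm paragraph and the unqualified statement on immediate bronchodilator treatment with home dosing. Which clinical procedure should apply at home is for the investigators to decide; this review proposes none. If the DSMP already covers it, a cross-reference is enough.
5. Reconcile the two anchors for the Week 1 call.

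The cost is two columns on a form that subjects already keep, plus protocol wording. The drawbacks are a little more subject burden and home data that are self-reported and possibly unblinded, which is a reason to show them separately as well as pooled.
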